9.4.2 Safety

The total sample size of 60 **participants** will be randomized at a 2:1 ratio to ruxolitinib:no study treatment ratio, results in 40 **participants** receiving ruxolitinib and 20 receiving no study treatment. The 40 ruxolitinib-treated **participants** will provide 90% probability of observing an AE that would occur in 6% or more of treated **participants**.

We assume the rate of events (outlined in 9.2.1.1) in the no study treatment arm will be no more than 2%. Assuming this rate in the no study treatment arm, we will have 80% power to detect a significant difference between the two arms, via a one-sided Fisher's exact test with 5% alpha, if the rate in the ruxolitinib arm is 27%.

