## 2.4 Outcome measures

### 2.4.1 Primary Outcome Measures

#### Safety

- 1) Proportion of participants on the *Ruxolitinib arm* who experience any of the following safety milestones while on-treatment:
  - o For participants with entry CD4+ T cell count  $< 700 \text{ cells/mm}^3$ , confirmed CD4+ decline  $> 33\%$  of baseline and to  $< 350 \text{ cells/mm}^3$ .
  - o For participants with entry CD4+ T cell count  $\geq 700 \text{ cells/mm}^3$ , a confirmed CD4+ T cell decline  $> 50\%$  of baseline.
  - o Confirmed HIV-1 RNA level above the lower limit of quantification in the absence of an interruption in ART.
  - o New or recurrent CDC category C AIDS-indicator condition.
  - o HIV-1 associated infection including Herpes zoster.
  - o Lymphoproliferative malignancies.
  - o Discontinuation of ruxolitinib due to thrombocytopenia.
  - o Grade 4 or recurrence of Grade 3 anemia/neutropenia.
  - o Any Grade 4 or recurrence of Grade 3 toxicity related to study drug.
  - o New diagnosis of pneumonia, sepsis, or bacteremia.
- 2) Proportion of participants who experience any of the following safety milestones on-study from entry through week 5 by study arm:
  - o For participants with entry CD4+ T cell count  $< 700 \text{ cells/mm}^3$ , confirmed CD4+ decline  $> 33\%$  of baseline and to  $< 350 \text{ cells/mm}^3$ .
  - o For participants with entry CD4+ T cell count  $\geq 700 \text{ cells/mm}^3$ , a confirmed CD4+ T cell decline  $> 50\%$  of baseline.
  - o Confirmed HIV-1 RNA level above the lower limit of quantification in the absence of an interruption in ART.
  - o New or recurrent CDC category C AIDS-indicator condition.
  - o HIV-1 associated infection including Herpes zoster.
  - o Lymphoproliferative malignancies.
  - o Occurrence of Grade 2 or higher thrombocytopenia.
  - o Grade 4 or recurrence of Grade 3 anemia/neutropenia.
  - o Any Grade 4 or recurrence of Grade 3 toxicity.
  - o New diagnosis of pneumonia, sepsis, or bacteremia.

- 3) Proportion of *each* of the following components that occurred on-study from entry to week 5 by study arm:
- o For participants with entry CD4+ T cell count  $< 700$  cells/mm^3, confirmed CD4+ decline  $> 33\%$  of baseline and to  $< 350$  cells/mm^3.
  - o For participants with entry CD4+ T cell count  $\geq 700$  cells/mm^3, a confirmed CD4+ T cell decline  $> 50\%$  of baseline.

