### 3 General Analysis Considerations

Study entry is defined as the date of the entry visit recorded on study initiation case report form.

The protocol-defined study week windows are modified for analysis purposes. For all analyses, the following window definitions will be used:

Pre-entry:	The last visit that occurred at least 24 hours prior to entry, but not more than 7 days before
Entry:	The visit after randomization, and prior to initiation of study treatment: Days [0-3]
Week 1:	The first visit in the window: Days [4, 22]
Week 2:	The second visit in the window: Days [4, 22]
Week 4:	The first visit in the window: Days [25, 39]
Week 5:	The second visit in the window: Days [25, 39]
Week 10:	The first visit in the window: Days [56, 93]
Week 12:	The second visit in the window: Days [56, 93]

Baseline values are the average of pre-entry and entry values, the week 4/5 values are the average of week 4 and week 5 values, and the week 10/12 values are the average of week 10

and 12 values; averages will be calculated using geometric means for log-transformed data and arithmetic mean for non-transformed data. If missing one of the pre-entry or entry values, then the available measure will be used as the baseline value, and similarly, if missing one of the week 4 or week 5 values or week 10 or week 12 values, then the available measure will be used as the week 4/5 value or week 10/12 value, respectively.

Analyses will be done among those in the as-treated population or among those in the safety analysis population (Cameron 2008), depending on the outcome; see the Statistical Methods section for details on populations for specific outcomes. The safety analysis population will consist of all participants randomized to the no-treatment arm and all participants who took at least one dose of ruxolitinib among those randomized to the ruxolitinib arm. The as-treated population is defined as participants who meet the following conditions: (1) have data at baseline and week 4/5, (2) for the ruxolitinib arm, remained on study treatment through week 4/5 and missed no more than 6 doses cumulatively, (3) did not change ART, use prohibited medications, or had confirmed virologic failure in this time period. Participants found to be ineligible after enrollment will be included in all safety analyses, but excluded from other analyses.

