## 4 Statistical Methods

### 4.1 Primary Outcome Measures

#### 4.1.1 Safety

Tabular summaries of all primary safety outcomes will be provided for primary outcomes (1), (2), and (3), which will include frequencies and percentages overall and by study arm. Formal comparisons between study arms will contrast the proportion of participants who experienced any safety milestones on study from entry through week 5 as defined in primary outcome (2) using a one-sided mid-p Fisher's exact test with 5% type-I error.

All safety summaries will be done in the safety analysis population.

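### The safety population keeps every Arm B participant but only dosed Arm A participants, so an Arm B participant who leaves before treatment would start stays in the milestone denominators and by default counts as event-free

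*SAP*

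**What the plan says.** SAP section 3 sets two entry conditions for the safety analysis population, which is to consist of "all participants randomized to the no-treatment arm and all participants who took at least one dose of ruxolitinib". For Arm B it takes everyone randomized. For Arm A it takes only those "who took at least one dose of ruxolitinib among those randomized to the ruxolitinib arm". SAP 4.1.1 then states: "All safety summaries will be done in the safety analysis population".

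The outcome compared is primary outcome (2) in SAP 2.4.1: "Proportion of participants who experience any of the following safety milestones on-study from entry through week 5 by study arm". The test is a "one-sided mid-p Fisher's exact test with 5% type-I error". SAP 4.2.1 repeats the test, in the same population, for milestones through week 12.

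Three protocol provisions matter here:
- Entry evaluations follow randomization and precede treatment, and treatment must begin within 72 hours of enrollment (6.2.2).
- Arm A participants who never start treatment need no follow-up beyond entry (6.2.4).
- The sample-size text assumes that the control event rate "will be no more than 2" percent (9.4.2).

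The only visible rule for incomplete milestone data is in SAP section 3. It counts a suspected virologic failure without a confirmatory test as confirmed, which requires that an elevated value exists.

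**The concern.** Participants know their arm once randomized, and some may leave at that point. In Arm A such a person drops out of the safety analysis. In Arm B the same behaviour leaves a person with no post-entry data in a denominator of about 20. The outcome is a simple proportion, with no censoring and no minimum follow-up, so someone with no data has no recorded milestone and is scored as not having had one.

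The Arm B rate would then be too low and the contrast would be tilted towards a ruxolitinib harm signal, in an analysis that serves a primary objective. For efficacy, the SAP avoids the problem by requiring baseline and week 4/5 data in both arms. Safety has no counterpart.

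**Working it through.** **Inputs.** 40 v 20 participants (SAP 2.1); one-sided mid-p Fisher test at 5% (SAP 4.1.1); 27% v 2% (protocol 9.4.2). The number k of Arm B participants with no post-entry data is not in the documents. Values of 1, 2 and 4 are assumed.

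**Method.** With a events of n₁ in Arm A and b of n₂ in Arm B, let X be hypergeometric (population n₁+n₂, a+b events, n₁ drawn). Then

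mid-p = P(X > a) + ½·P(X = a).

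The rejection probability is the sum of the binomial probabilities of all (a, b) with mid-p ≤ 0.05. For leavers kept as event-free, b comes from 20−k people but n₂ = 20. For leavers excluded, n₂ = 20−k.

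**The plan's own figure.** Protocol 9.4.2 says "we will have 80% power to detect a significant difference between the two arms, via a one-sided Fisher's exact test with 5% alpha" at 27% v 2%. Exact enumeration with the ordinary Fisher test gives 78.4%, close to the stated 80%. The SAP's mid-p version gives 88.9%.

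**Bias in the Arm B rate.** Expected observed rate = true rate × (20−k)/20. With k = 1 the factor is 0.95, and with k = 4 it is 0.80. At a true 2% and k = 4 this is 2% × 0.80 = 1.6%, a shift of 0.4 points.

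**Type I error, equal true rates, no loss in Arm A (kept as event-free / excluded):**

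| True rate | k = 0 | k = 1 | k = 2 | k = 4 |
|---|---|---|---|---|
| 2% | 0.01% | 0.01 / 0.01% | 0.01 / 0.01% | 0.01 / <0.01% |
| 10% | 2.94% | 3.24 / 2.93% | 3.57 / 3.25% | 4.34 / 1.89% |
| 15% | 4.34% | 4.96 / 3.73% | 5.67 / 4.30% | 7.39 / 3.56% |
| 20% | 4.69% | 5.54 / 3.89% | 6.52 / 4.50% | 9.00 / 4.00% |

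**Loss in both arms, everyone kept in the denominator:**

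| Loss | True rate 15% | True rate 20% |
|---|---|---|
| 10% in each arm | 3.95% | 4.45% |
| 20% in each arm | 3.48% | 4.13% |
| 4 of 40 in Arm A, 3 of 20 in Arm B | 4.55% | 5.29% |

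Equal loss removes the inflation. Only the excess in Arm B matters.

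**One person near the boundary.** Take 9/40 v 1 event in Arm B.
- Denominator 20: P(X = 10) = C(40,10)/C(60,10) = 0.0112. P(X = 9) = 20·C(40,9)/C(60,10) = 0.0725. Mid-p = 0.0112 + 0.0363 = 0.0475.
- Denominator 19: C(40,10)/C(59,10) = 0.0135. 19·C(40,9)/C(59,10) = 0.0827. Mid-p = 0.0135 + 0.0413 = 0.0548.

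One retained leaver moves this result across 0.05.

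**The case against.** The strongest reply has four parts.

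1. **The window is short.** The arms differ only for loss before the first dose, which is due within 72 hours of enrollment. An Arm A participant who takes one dose and is never seen again is also kept without data. A reader might infer that only Arm B can contain unascertained people. The documents do not support that, because loss after dosing is handled alike in both arms. This part stands and limits the point.

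2. **The larger error rates rest on unsupported inputs.** A reader might apply the protocol's 20% attrition to Arm B and quote 7.4% or 9.0%. That allowance (9.4.1) belongs to the IL-6 analysis, covers both arms, and includes drug discontinuation, which Arm B cannot have. The figures also need zero loss in Arm A and true rates of 15% to 20%, against a planned control rate of at most 2%. This stands. However, the between-arm composite counts any Grade 4 or recurrent Grade 3 toxicity and any Grade 2 or higher thrombocytopenia, regardless of relatedness. The 2% is therefore an assumption.

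3. **The event-free scoring is inferred.** The SAP never states it, and the implementation plan in Appendix 2 is redacted and may hold a rule. This stands as a caveat. The difference in the population definition is nevertheless in the visible text.

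4. **The bias overstates harm and does not hide it, and restricting Arm A to dosed participants is reasoned.** Both are true. Neither explains why Arm B has no matching contact requirement.

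A reader might also think that the week 5 comparison is the only formal safety test. It is not: SAP 4.2.1 adds the week 12 milestone test, which shares the problem, and t-tests on changes in safety laboratory values. The t-tests need a post-entry measurement, so the default scoring cannot enter them.

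**Conclusion.** The point holds as a minor one. The entry rule differs by arm and, absent a rule in the redacted appendix, can bias the Arm B milestone rate downward at weeks 5 and 12. The size depends on the number of Arm B leavers before treatment start in excess of unascertained Arm A participants, and on the true event rate. Type I error is unaffected at 2%, below 5% at rates up to 10% even with four leavers, and about 5% to 5.5% at rates of 15% to 20% with one leaver. The documents do not show that any such participant exists, and they do not support a claim of substantial inflation or of concealed harm.

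**What to change.** In SAP section 3, add a population for the between-arm comparisons (primary outcomes 2 and 3, secondary outcomes 2 to 4) with the same contact rule in both arms: at least one post-entry study visit or scheduled safety laboratory assessment, plus at least one ruxolitinib dose in Arm A. A reported event alone should not qualify, because that would make inclusion depend on the outcome. Keep all dosed participants for the Arm A-only outcomes. Report the number excluded per arm in the CONSORT diagram that SAP section 5 already plans, and show the current definition as a sensitivity analysis.

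The cost is one sentence, one sensitivity line and no new data. A few participants in either arm may leave the between-arm denominator, including any dosed Arm A participant with no later contact, with a slight loss of power. At 27% v 2%, mid-p power is 88.9% with all 20 controls. It is 85.6%, 86.2% and 81.2% with 1, 2 and 4 controls excluded, still above the planned 80%. If nobody is lost early, nothing changes.

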## 4 Statistical Methods

### 4.1 Primary Outcome Measures

#### 4.1.1 Safety

Tabular summaries of all primary safety outcomes will be provided for primary outcomes (1), (2), and (3), which will include frequencies and percentages overall and by study arm. Formal comparisons between study arms will contrast the proportion of participants who experienced any safety milestones on study from entry through week 5 as defined in primary outcome (2) using a one-sided mid-p Fisher's exact test with 5% type-I error.

All safety summaries will be done in the safety analysis population.

#### **4.1.2 Tolerability**

All tolerability summaries will be done in the safety analysis population.

Participant-level listings of occurrences of premature discontinuation of study treatment will be provided, including reasons for discontinuation. If a given reason for premature discontinuation occurs in more than 5 participants, then tabular summaries including frequency and percentages will also be provided. This summary will only be provided for those in the Ruxolitinib arm.

#### **4.1.3 Efficacy**

The primary efficacy analyses will be done in the as-treated population.

Analyses addressing efficacy of ruxolitinib will contrast IL-6 changes from baseline to week 4/5 between study arms. Baseline and week 4/5 are defined based on the criteria mentioned in the General Analysis Considerations section and IL-6 will be transformed to the log-10 scale for all analyses.

Formal study arm comparisons will contrast the mean change from baseline to week 4/5 between study arms. The mean and 90% confidence interval (CI) for the mean change will be calculated; corresponding p-value based on a two-sided t-test with 10% alpha will also be calculated.

Descriptive summaries of levels of IL-6 at baseline and week 4/5 will be presented by study arm using continuous summary statistics and longitudinal plots. Changes in IL-6 (log10) from baseline to week 4/5 will be summarized with the mean and a 95% CI for the change separately within each study arm; change will be presented as absolute mean log10 change and corresponding geometric mean fold-change.

### **4.2 Secondary Outcome Measures**

#### **4.2.1 Safety**

All summaries of secondary safety outcomes will be done in the safety analysis population.

In a similar manner to the primary safety analyses, tabular summaries will be provided for secondary outcomes (1-4), which will include frequencies and percentages overall and by study arm. Formal comparisons between study arms will contrast the proportion of participants who experienced any safety milestones on study from entry through week 12 as defined in secondary outcome (2) using a one-sided mid-p Fisher's exact test with 5% type-I error.

Levels and changes in safety laboratories (secondary outcomes 5 and 6) will be summarized with continuous descriptive summary statistics. Changes in safety labs will be formally compared at week 4/5 and week 10/12 via two-sided t-tests with 10% alpha and corresponding 90% confidence intervals.

#### **4.2.2 Longitudinal Summaries of CD4 Count and plasma HIV-1 RNA**

Descriptive longitudinal summaries of levels and changes in CD4 cell counts and CD4 % will be provided by study arm and week. Formal comparisons between study arms of change from baseline will occur at all post-entry visits (week 2, 5, and 12); two-sided t-tests with 10% alpha will contrast differences between groups. In addition, change from week 5 (end of treatment) to week 12 (end of study) will also be examined. Participant narratives will be provided for those who had a protocol defined drop in CD4 cell counts (see primary safety endpoint).

Tabular summaries of categorized HIV-1 RNA levels (secondary outcome 10) by study week and arm will also be provided; no statistical inference will be done. HIV-1 RNA levels will be categorized as below or above the lower limit of quantification. Participant narratives will be provided for those who had any viral loads above the lower limit of quantification while on study.

All summaries will be done in the safety analysis and as-treated populations.

#### **4.2.3 Immune Activation and Inflammation**

The immunology markers outlined in secondary outcome measures (7-9) will be addressed in the following manner. All analyses will be done in the as-treated population, and geometric means will be used to average pre-entry and entry, week 4 and 5, and week 10 and 12, as available. As mentioned in the General Analysis Consideration section, biomarkers will be log-10 transformed as appropriate.

Descriptive summaries of levels and changes (absolute changes and corresponding fold-changes) will be done using continuous summary statistics and longitudinal plots by study week and arm. Treatment group comparisons will contrast the change from baseline at each post-entry study week using two sided t-tests with 10% alpha; corresponding p-values and 90% CIs will also be calculated. In addition, change from end of treatment to end of study will also be examined in a similar manner. Results for log-10 transformed markers will be back transformed to fold-changes for presentation as appropriate.

#### **4.2.4 HIV-1 Reservoir**

Tabular summaries of categorized HIV-1 RNA by iSCA (secondary outcome 12) will be provided by study week and arm. To compare changes in iSCA over time and between study arms, a GEE model for binary data will be used since it is anticipated that a substantial proportion of the data will be below assay limit (Riddler 2016).

Total HIV-1 DNA and cell-associated HIV-1 RNA will be log-10 transformed and summarized by arm and across study weeks with continuous summary statistics and longitudinal plots, imputing values below the assay limit as the lower limit of the assay; as with the immunology markers, results will be back-transformed to fold-changes for presentation. Total HIV-1 DNA and cell-associated HIV-RNA will also be summarized categorically as the frequency and percent below or above the lower limit; if there are differential assay lower limits, an analytic lower limit will be applied for this summary.

Results below assay limit are not anticipated for total HIV-1 DNA (Gandhi 2017). Changes from baseline will be contrasted between study arms using a two-sided t-test with 10% alpha at each visit (week 5 and week 12); in addition, a comparison between week 5 (end of treatment) and week 12 (end of study) will also be done.

Modest amounts of below assay limit observations are anticipated for cell-associated HIV-1 RNA (Gandhi 2017). To contrast changes over time between study arms, a longitudinal censored normal model approach will be used, which was developed for below assay limit HIV virology data and can handle different assay limits (Riddler 2016, Vaida 2009).

In the event that a large proportion of participants have values below assay limits for total HIV-1 DNA and cell-associated HIV-1 RNA, a binary analysis approach similar to the analysis of iSCA will be used.

All analyses will occur in the as-treated population. For GEE and longitudinal censored normal models, the analysis will also be restricted to those who have results for corresponding time points of interest.

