7.5 Confirmed Virologic Failure

In the event of confirmed virologic failure, defined as the occurrence of two sequential plasma HIV-1 RNA values above the lower limit of quantification in the absence of an interruption in ART, the study drug must be stopped for participants in Arm A. The participant will be followed on study with all evaluations performed through week 12. If the participant does not agree to continue on study, then the premature study discontinuation evaluations should be completed.

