### 2.3.2 Secondary Objectives

- 1) To evaluate the safety of ruxolitinib in ART-treated HIV-1 infected virologically suppressed participants during all on-study visits through week 12 [Protocol Objective 1.3.1].
- 2) To compare changes in IL-6 levels between baseline and week 12 in ART-treated HIV-1 virologically suppressed participants who are randomized to ruxolitinib to changes in those participants randomized to receive no study treatment [Protocol Objective 1.3.2].
- 3) To assess whether the use of ruxolitinib will decrease levels of other measures of inflammation and immune activation including sCD14, tumor necrosis factor alpha (TNF- $\alpha$ ), IL-1 $\alpha$ , IL-1 $\beta$ , IL-18, macrophage colony stimulating factor (mCSF), neopterin, HLA-DR, CD38, and both the distribution of monocyte subsets (defined by expression of CD14+ and CD16+) and phenotypic indices of their activation during 5 weeks of treatment and at week 12 [Protocol Objective 1.3.3].

- 4) To examine whether the use of ruxolitinib is associated with changes in HIV-1 plasma viral load levels (by a commercial clinical assay and single-copy assay) and CD4+ T cell counts in HIV-1 infected participants at baseline compared to 12 weeks after initiation of treatment for those receiving 5 weeks of ruxolitinib versus those receiving no study treatment [Protocol Objective 1.3.4].
- 5) To assess changes from baseline in the HIV-1 reservoir, specifically plasma HIV-1 RNA by single copy assay (as above), cellular HIV-1 RNA and total DNA, 2 long-terminal repeat sequences [LTRs], and integrated DNA [Protocol Objective 1.3.5].
- 6) To evaluate whether the use of ruxolitinib is associated with more frequent reactivation of human herpes viruses (ie, cytomegalovirus [CMV], Epstein Barr virus [EBV], herpes simplex viruses [HSV], human herpes viruses [HHV] 6, 7, and 8) as measured in longitudinally collected oral swabs [Protocol Objective 1.3.7].

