Confirmed virologic failure is defined as the occurrence of two sequential plasma HIV-1 RNA values above the lower limit of quantification in the absence of an interruption of ART; the confirmatory HIV-1 RNA should occur within 7 days of receipt of the results for the first test. In the event that a suspected virologic failure is not confirmed with a follow-up HIV-1 RNA test (i.e., there is no subsequent HIV-1 RNA available), this suspected virologic failure will be considered a *confirmed* virologic failure. Confirmed CD4 count decline is defined as two sequential CD4 counts meeting the respective criteria in the absence of an interruption in ART. Adverse events are classified as related (definitely, probably, possibly) or not related (probably not, not) by site investigators.

Biomarker data distributions will be assessed for normality, and any non-normal data will be log-transformed to the log-10 scale for analysis; it is anticipated that all soluble markers will be log-transformed. Descriptive summaries of continuous baseline characteristics will include frequency, frequency missing, mean, sd, median, IQR, 10th and 90th percentiles, and min/max; descriptive summaries of other continuous variables will use mean and sd, or median and IQR depending upon the corresponding analysis method. The frequency and percentage will be used for all categorical variables.

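### SAP 4.2.4 compares single-copy RNA, cell-associated RNA and HIV-1 DNA only in a set that excludes virologic failure through week 4/5, which biases those comparisons toward no increase

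*SAP*

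**What the plan says.** SAP 2.3.2, objectives 4 and 5, asks whether ruxolitinib is associated with changes in plasma HIV-1 RNA (single-copy assay included), cell-associated RNA and HIV-1 DNA. SAP 4.2.4 gives the between-arm methods:

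- Single-copy RNA: "To compare changes in iSCA over time and between study arms, a GEE model for binary data will be used".
- Total HIV-1 DNA: two-sided t-tests at 10% alpha at weeks 5 and 12.
- Cell-associated RNA: a longitudinal censored normal model.

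The analysis set for all of them is fixed by "All analyses will occur in the as-treated population". No companion analysis in another set is planned there.

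SAP section 3 defines the as-treated set. Besides data at baseline and week 4/5, two conditions matter here:

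- Treatment: "for the ruxolitinib arm, remained on study treatment through week 4/5 and missed no more than 6 doses cumulatively".
- Virology and medication: participants who "did not change ART, use prohibited medications, or had confirmed virologic failure in this time period". The time period is baseline to week 4/5.

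Confirmed failure is "the occurrence of two sequential plasma HIV-1 RNA values above the lower limit of quantification in the absence of an interruption of ART". One further rule widens it: "In the event that a suspected virologic failure is not confirmed with a follow-up HIV-1 RNA test", the suspected failure is counted as confirmed. On confirmed failure, Protocol 7.5 says "the study drug must be stopped for participants in Arm A", with follow-up and all evaluations continuing through week 12.

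**The concern.** The exclusion is made after randomisation and depends on the quantity under test. Confirmed failure is a rise in plasma HIV-1 RNA, and single-copy RNA measures the same thing on a finer scale. Cell-associated RNA is a related marker of virus production. The condition can only remove rises, never falls. If ruxolitinib raised virus production in some participants, those with the clearest rises would leave Arm A before the arms were compared. Because membership is settled at week 4/5, they are also lost from the week 12 and week 5-to-12 comparisons.

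The stated reason for the as-treated set does not carry over. Protocol 9.6.1 adopts it for the primary efficacy analysis, IL-6, where setting aside participants with viremia is defensible because viremia itself affects inflammation. Protocol 9.6.2 does not call for it for reservoir outcomes. An increase is a possible result: Protocol 2.1 calls the drug's effect on the balance between latent and transcribed HIV-1 DNA unknown.

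**Working it through.** **The plan's own figure.** The only sample size tied to the as-treated set is in Protocol 9.4.1: 60 × (1 − 0.20) = 48 evaluable, which at 2:1 is 32 in Arm A and 16 in Arm B. It reproduces. The IL-6 power for that size is 82.4% by noncentral t (difference 0.20, SD 0.25, two-sided alpha 0.10), or 81.1% with the unrounded SD of 0.2548, against the stated 80%. No power is stated for single-copy or reservoir outcomes.

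**Who is removed.** Plasma HIV-1 RNA is scheduled at weeks 2 and 5 during treatment (Protocol 6.1).

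| Event | Arm A | Arm B |
|---|---|---|
| Value above limit at week 2, confirmed | Out twice: failure condition, and drug stopped | Out: failure condition |
| Value above limit by week 5, never retested | Out: failure condition | Out: failure condition |
| First value at week 5, confirmed later | Not stated whether this falls in the period | Same |
| Failure after week 5 | Stays in | Stays in |
| Rise below clinical limit, or retest below limit | Stays in | Stays in |

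**Number of failures.** Protocol 9.5 stops dosing for everyone if more than 2 Arm A participants have confirmed failure. Two can therefore occur with the trial running on, and I use 2. The detection rates and rises below are assumptions.

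**Single-copy detection, failures counted within the 32.** If 14 of 32 are detectable and both failures are among them, removing them gives 12/30:

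- 14/32 = 43.8%; 12/30 = 40.0%; change about 3.8 points.

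**Single-copy detection, failures added to 32:16.** With equal detection in both arms before the failures return, and each failure detectable:

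| Starting rate | Arm B | Arm A plus 1 | Arm A plus 2 |
|---|---|---|---|
| 31% (10/32) | 5/16 | 11/33, +2.1 points | 12/34, +4.0 points |
| 50% (16/32) | 8/16 | 17/33, +1.5 points | 18/34, +2.9 points |
| 69% (22/32) | 11/16 | 23/33, +0.9 points | 24/34, +1.8 points |

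**Cell-associated RNA.** If two of 32 have a rise d above the others' mean change, removing them lowers the simple arm mean by 2d/32. For d = 0.5 this is 0.031 log10; for d = 1.0 it is 0.062 log10. The planned censored model is not a simple mean, so this is a guide only.

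**Scale against noise.** With 43.8% detectable in both arms, the standard error of the difference is √(0.4375 × 0.5625 × (1/32 + 1/16)) = 0.152, about 15 points.

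**Simulation.** I assumed 40:20, failures only in Arm A at 5% (2 expected), every failure detectable, and a two-sided 10% test of proportions standing in for the GEE. Keeping failures gives a mean difference of about +3 points at 30% background detection and +2.5 at 50%, with rejection of 11.5% in both. Dropping them gives about 0, with rejection of 10.1% and 11.0%. Any effect acting only through overt failure disappears from the as-treated estimate, though at this failure rate power is low either way.

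**The case against.** The strongest reply is that failures are not lost from the trial's results. Confirmed HIV-1 RNA above the limit is a component of the primary safety composite, which is tested between arms in the safety population, reported by component, and repeated through week 12 (SAP 2.4.1, 2.4.2, 4.1.1, 4.2.1). SAP 4.2.2 tabulates clinical-assay RNA in both the safety and as-treated populations and requires narratives for any value above the limit. Protocol 9.5 adds the study-wide dosing stop. All of this stands. A reader might infer from 4.2.4 that a virologic harm signal is hidden, and the documents do not support that. What these analyses do not provide is a comparison of single-copy RNA, cell-associated RNA or HIV-1 DNA that includes the failures.

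A reader might also infer that everyone whose HIV-1 RNA rose, or everyone with virologic failure, is cut. That is too broad. The condition ends at week 4/5, so later failures are analysed at week 12, the time point named in objective 4. Rises below the clinical limit, which a single-copy assay is meant to detect, stay in.

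A third temptation is to model continuous log10 RNA with values above the limit removed, which can suggest a much larger loss. The SAP does not compare continuous single-copy values; it analyses them as binary.

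Finally, these are secondary outcomes without stated power, and the illustrated shifts are small against a standard error of about 15 points. That limits the importance of the point but does not justify the choice of set.

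**Conclusion.** The point holds for the comparisons in SAP 4.2.4 and no further. Their analysis set is selected on a post-randomisation rise in plasma HIV-1 RNA, and no companion analysis offsets it. The bias is toward no increase on ruxolitinib, provided failures through week 4/5 are commoner in Arm A; equal failure rates would largely cancel in the contrast.

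The size cannot be derived from the documents, which give neither a failure rate nor a single-copy detection rate. With 2 Arm A failures, the illustrations give roughly 2 to 4 percentage points of detection and 0.03 to 0.06 log10 in mean cell-associated RNA. With no failures through week 4/5, this exclusion has no effect. The change is worth making because the direction under drug-related failure is predictable and the remedy is cheap.

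**What to change.** In SAP 4.2.4, analyse secondary outcome 12 and the reservoir items in 2.4.3 by randomised arm in all participants with available specimens, regardless of virologic failure or the resulting drug discontinuation. SAP 4.2.5 already takes all available specimens for CMV. Report the as-treated version alongside, and state whether a first elevated value at week 5 that is confirmed later counts as failure in the period.

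Deleting only the virologic-failure condition would not be enough. An Arm A failure found at week 2 and confirmed would stay out through the on-treatment condition, while the matching Arm B participant would return, making the arms less comparable.

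The cost is a short SAP change, one extra analysis run, assays for any stored samples not yet tested, and some dilution from participants who stopped drug. The samples should exist: single-copy and reservoir specimens are scheduled at entry and weeks 5 and 12, and failures are followed through week 12. Leave the IL-6 and immune-marker sets unchanged.
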